### **10.5.7.4 PK Analysis**

PK will be analyzed retroactively if possible, using back up blood samples at the following timepoints- before the first dose at Day 1 (Visit 2), Day 29 (Visit 3), Day 85 (Visit 5), Day 155 (Visit 8), and Day 197 (Visit 10)/End or Study/Early Termination).

## **10.5.8 Urinalysis**

A midstream urine sample (approximately 30 mL) will be obtained in order to avoid contamination with epithelial cells and sediments and allow proper assessments.

Semi-quantitative “dipstick” evaluation for specific gravity, glucose, protein, bilirubin, ketones, leukocytes and blood will be performed at site. When a dipstick evaluation is abnormal, e.g., positive for WBC and/or blood, a urine sample needs to be sent to the lab for microscopic examination including RBC and WBC. Details on collection of urine for analysis are provided to Investigators in the Laboratory Manual.

### **10.5.8.1 Urine Drug Screen and Cotinine Test**

Urine samples will be collected at Screening for urine drug screening (alcohol, amphetamines/methamphetamines, barbiturates, benzodiazepines, cannabinoids, cocaine, cotinine, methadone, methaqualone, opiates, phencyclidine) and urine cotinine tests.

## **10.5.9 Fecal Collection**

Fecal collection kits will be provided to subjects during Screening for ova and parasite tests. Subjects will return the sample to the clinical site during the Screening period (Days -28 to -7).

## **10.5.10 Electrocardiogram**

Standard 12 lead electrocardiograms (ECGs) must be recorded after 10 minutes rest in the supine position to ensure a stable baseline. The preferred sequence of cardiovascular data collection during study visits is: ECG collection first, followed by vital signs, and blood sampling. The

ECGs will be recorded at Visits 1, 2, 3, 4, 5, 6, 7, 8, 9, and 10. The print-outs will be generated and kept at the Investigator site as source documentation. Clinically significant ECG findings prior to dosing with AK002 must be reviewed by the Principal Investigator and/or cardiologist. Clinically significant abnormalities should be recorded on the relevant section of the Medical History/Current Medical Conditions/AE CRF page, as appropriate.

#### **10.5.11 Pregnancy Testing**

All women of childbearing potential will have a serum pregnancy test and urine pregnancy tests at the visits specified in [Table 3](#). A positive urine pregnancy test requires immediate interruption of study medication until serum B-hCG is performed and found to be negative. If positive, the patient must be discontinued from the study. Urine pregnancy test kits will be provided to the sites by the Central Lab.

To ensure patient safety, each pregnancy in a patient on study drug must be reported within 24 hours of learning of its occurrence. The pregnancy should be followed up to determine outcome, including spontaneous or voluntary termination, details of the birth, and the presence or absence of any birth defects, congenital abnormalities, or maternal and/or newborn complications. Any SAE experienced during pregnancy must be reported on the SAE Report Form.

#### **10.5.12 Tolerability/Acceptability**

Other than adverse events, no specific tolerability/acceptability data are collected.

### **10.6 End of Trial**

End of trial is defined as last patient, last visit.

## **11. Adverse Event Reporting**

All adverse events will be collected starting from the time of first AK002 infusion and until the end of the follow-up period or the Early Termination Visit, unless directed otherwise by Allakos.

In accordance with 21 Code of Federal Regulation (CFR) 312.32(b) and International Conference on Harmonisation (ICH) Guidance E2A, an AE is any untoward medical occurrence in a clinical investigation of a patient administered a pharmaceutical product and that does not necessarily have a causal relationship with the treatment. An AE is therefore any unfavorable and unintended sign (including an abnormal laboratory finding), symptom or disease temporally associated with the administration of an investigational product, whether or not related to that investigational product. An unexpected AE is one of a type not identified in nature, severity, or

frequency in the current Investigator's Brochure or of greater severity or frequency than expected based on the information in the Investigator's Brochure.

Events that do not meet the definition of an AE include:

- Medical or surgical procedure (e.g., endoscopy, appendectomy); the condition that leads to the procedure is an AE.
- Situations where an untoward medical occurrence did not occur (e.g., social and/or convenience admission to a hospital).
- Anticipated day-to-day fluctuations of pre-existing disease(s) or condition(s) present or detected prior to first study drug infusion that do not worsen.
- Significant reductions in numbers of eosinophils or basophils in blood count, as these are expected therapeutic effects of the study drug.

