Centers/Countries	Approximately 4 study centers in the USA and Germany. Only the sites in Germany will participate in the extension study.
Number of Subjects	
N (total) = Approximately 48 subjects with chronic urticaria
 
This will include the following cohorts:
 
 
• Approximately 12 subjects with Cholinergic urticaria (CholU)
 
• Approximately 12 subjects with Urticaria factitia (UF)
 
• Approximately 12 XOLAIR® (omalizumab) naïve subjects with Chronic spontaneous urticaria (CSU)
 
• Approximately 12 subjects with Chronic spontaneous urticaria (CSU) who did not achieve an adequate response on XOLAIR® (omalizumab) in the opinion of the Investigator
 
 
The extended dosing will be applicable only to the subjects in the CholU, UF, and CSU-XOLAIR® (omalizumab) failure cohorts.

Rationale for Sample Size	The planned sample size of approximately 48 subjects is based on common practice in early phase, proof-of-concept studies.
Duration of Patient Participation and Duration of Study	
The total study duration for each patient will be approximately 32 weeks. This includes:
 
 
• A screening period of 4 weeks prior to study drug administration
 
• Administration of study drug at Day 1, Day 29, Day 57, Day 85, Day 113, and Day 141
 
• Follow-up through Day 197 (8 weeks post last dose)
 

Duration of Patient Participation and Study cont.	Subjects who elect to receive optional extended dosing with up to 12 additional doses of AK002 will participate for up to an additional 12 months (see Appendix 2 ).

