Concomitant Medications	Second-generation H1-antihistamines as concomitant medication once daily and up to 4 times daily on demand (drug intake to be documented in the patient diary).
Safety Evaluations	
Safety and tolerability will be assessed throughout the study by monitoring and evaluating adverse events (AEs), including any complications resulting from the IV infusion. All treatment-emergent adverse events (TEAEs) will be collected from the start of study drug administration through 8 weeks after last dose received or Early Termination (ET). Severity will be assessed using the National Cancer Institute (NCI) Common Terminology Criteria for Adverse Events (CTCAE) Version 4.03. All AEs will be assigned a severity grade and relationship to study drug.
 
Additional safety evaluations include clinical laboratory tests, including anti-drug antibody to AK002, complete blood counts, chemistries, and urinalyses, ECGs; and vital signs.

Statistical Methodology	All subjects who received a dose of study drug will be included in the analysis. All safety data will be listed. Where appropriate, summary statistics will be provided (number of non-missing values, mean, median, standard deviation, minimum, and maximum for continuous variables, and number and percentage for categorical variables) for all measures, including demographic and baseline values, clinical scores and safety endpoints.
Rationale for Amendment 4.1	
The following modifications have been incorporated into Amendment 4.1 of the protocol.
 
 
• Procedures that allow subjects in the CholU, UF, and CSU-XOLAIR® (omalizumab) failure cohorts who received all 6 infusions of AK002, were followed through Day 155, and demonstrated severe symptoms of urticaria following discontinuation of treatment, to be offered the option to receive extended dosing with up to 12 additional doses of AK002. Offering extended dosing allows subjects with no other treatment options continued access to AK002 and the benefit obtained during the initial 6 infusions. It also allows for collection of longer-term efficacy, safety, and tolerability data of AK002.
 
• PK will be analyzed retroactively using backup blood samples.
 

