### **6.3 Rationale for the Dose/Regimen, Route of Administration, and Duration of Treatment**

#### **6.3.1 Rationale for AK002 Dose and Regimen**

The proposed AK002 dose of 0.3 mg/kg administered at Day 1 and increased to 1 mg/kg at Day 29, Day 57, and subsequently to 3 mg/kg on Days 85, 113, and 141 is based on prior experience with AK002 in healthy volunteers and in subjects with ISM. Also, the long-term continuation treatment will provide the option of an additional 12 months of treatment for patients with severe disease at baseline who recorded a complete response while on treatment with AK002 (1 mg/kg or 3 mg/kg) and who developed severe symptoms within 6 months of discontinuing AK002. The continuation protocol will be limited to patients who have no other treatment options, that is CholU, UF, or Xolair failures in patients with CSU.

Subjects with ISM receiving 0.3 mg/kg, 1 mg/kg, and 3 mg/kg AK002 have reported improvement of their clinical symptoms in a dose-dependent fashion. For example, some ISM patients who showed some response to 1 mg/kg, showed improved symptom control when the dose was increased to 3 mg/kg. In general, AK002 was well tolerated in these subjects. A dose of 0.3 mg/kg resulted in suppression of eosinophils for approximately 1 month, which would justify a monthly dosing regimen. In addition, a starting dose of 0.3 mg/kg has demonstrated an adequate safety and tolerability profile in previous and current clinical trials.

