## **9. Discontinuation and Replacement of Subjects and Major Protocol Deviations**

### **9.1 Definition of Early Termination from the Study**

A patient who discontinues the study before completing the Follow-Up visit at Week 28 is considered to have terminated early. All subjects who discontinue the study prior to completing the final Follow-Up visit should return to the site 28 ( $\pm 2$ ) days after the last dose of study drug or prior to this if necessary. If early termination occurs more than 28 days after the last dose of study drug, then perform the Early Termination Visit as soon as possible.

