## **10. Visit Schedule and Assessments**

[Table 3](#) shows the schedule of assessments by study visit. Subjects should be seen for all visits on the designated day or as close to it as possible.

Subjects discontinuing the study drug before completing the 12-week treatment period, and those who prematurely withdraw from the study for any reason, should be scheduled for an early termination visit as soon as possible, at which time all of the assessments listed for the final visit will be performed.

Subjects who discontinue AK002 treatment also should return for the final assessments. If they refuse to return or are unable to do so, every effort should be made to contact them or a knowledgeable informant by telephone to determine the use of rescue medication and to complete the [REDACTED].

At a minimum, they will be contacted for safety evaluations during the 28 days following the last dose of AK002, including the final contact at the 28-day point. Documentation of attempts to contact the patient should be recorded in the patient record.

All data obtained from the assessments listed in Table 3 and described in detail in the protocol must be supported in the patient's source documentation.

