## 17.2 Appendix 2: Procedures for Extended Dosing (Optional)

### Summary of Extended Dosing

Subjects in the CholU, UF, and CSU-XOLAIR® (omalizumab) failure cohorts who received all 6 infusions of AK002, were followed through Day 155, and demonstrated severe symptoms of urticaria following discontinuation of treatment will be allowed the option to receive extended dosing with up to 12 additional doses of AK002.

For extended dosing, subjects must have a baseline (Day 1) UCT of  $\leq 5$  and a week 22 (Day 155) UCT of  $\geq 12$  (Complete Response). They must have a UCT of  $\leq 5$  between Day 155 and Day 309 (i.e., within 6 months from last dose). All subjects that decide to receive the extended dosing will start with a dose of 0.3 mg/kg, followed by possible dose increases to 1 mg/kg and 3 mg/kg for subsequent infusions. The Investigator in consultation with the Medical Monitor may increase the dose to 6 mg/kg and then to 10 mg/kg if they think that the patient has not received benefit from the lower doses.

Extended dosing will include a Screening Period of 2 to 3 weeks, a Treatment Period of 44 weeks, and a Follow-up Period of 8 weeks after the last dose of study drug. During the Screening Period, subjects will receive a standard oral dose of a second-generation H1-antihistamine once daily, with on-demand dosing of up to 3 additional tablets per day. During the Treatment Period, subjects will continue daily dosing with the second-generation H1-antihistamine (standard dose once daily with on-demand dosing of up to 3 additional tablets per day) and AK002 administered by IV infusion on Extended Dosing Days 1, 29, 57, 85, 113, 141, 169, 197, 225, 253, 281, and 309. Subjects will be followed for 8 weeks after the last dose of study drug (Follow-up Period). Safety assessments and response to study drug will be evaluated throughout the study. The optional extended dosing period is outlined in [Table 8](#).

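### New adverse events are collected for 56 days after the last dose in completers but usually for only about 28 days in subjects who terminate early, and the SAP neither equalises nor shows the difference

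*Protocol*

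**What the plan says.** **End of collection.** Protocol Section 11 collects AEs "until the end of the follow-up period or the Early Termination Visit". The synopsis (Safety Evaluations) gives the window as "through 8 weeks after last dose received or Early Termination (ET"). Sections 11.4 (AESIs), 11.5 (SAEs) and 11.6.1 (eCRF recording) also end at the close of follow-up, Day 197 or the ET visit. Sections 11, 11.4 and 11.5 let the sponsor direct otherwise, but plan nothing further.

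**Timing of the ET visit.**
- Section 9.1: subjects "who discontinue the study prior to completing the final Follow-Up visit should return to the site 28" (±2) days after the last dose, or earlier if necessary. Those who terminate more than 28 days after the last dose have the visit as soon as possible.
- Section 9.3: subjects who stop study drug return at 28 (±2) days for procedures under a post-treatment follow-up heading that Table 3 does not carry. It does not say whether AE collection continues afterwards.
- Section 10: "Subjects discontinuing the study drug before completing the 12-week treatment period", and those who withdraw, "should be scheduled for an early termination visit as soon as possible". For subjects who discontinue AK002 it also sets a minimum of safety contact through the 28-day point. Its 12-week treatment period does not match dosing to Week 20 in Table 1.

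**Extension.** Appendix 2 states: "Subjects will be followed for 8 weeks after the last dose of study drug (Follow-up Period"). Table 9, note o, ends AE recording at Day 365 (±3), or at ET 28 (±3) days after the last dose.

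**SAP.** Section 4 defines a treatment-emergent AE (TEAE) by onset on or after the first dose, with no end point relative to the last dose. Section 7.10.1 reports n and % of subjects. Section 7.6.1 measures exposure from first to last dose, so it does not show follow-up after the last dose.

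**The concern.** The ET visit both ends a subject's participation and closes AE collection, so the length of post-dose observation depends on whether the subject completed. Subjects who leave because of toxicity are those in whom post-dose safety is most informative, and they usually have the shorter window. The loss would fall on new AEs, on new SAEs that bear on the trial-level criteria in Section 12.2, and on AESIs such as opportunistic and parasitic infections and hypersensitivity reactions.

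This matters because Section 13.8 expects the study to pick up major safety signals, and SAP 2.1 makes safety part of the primary objective. Section 6.3.1 adds some plausibility to late effects: "A dose of 0.3 mg/kg resulted in suppression of eosinophils for approximately 1 month", and later doses are higher. A crude n (%) that mixes 56-day and 28-day follow-up does not show the reader who was observed for how long.

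**Working it through.** **1. The plan's own figure.** The synopsis gives "Administration of study drug at Day 1, Day 29, Day 57, Day 85, Day 113, and Day 141" and follow-up to Day 197, stated as 8 weeks after the last dose.
- 197 − 141 = 56 days, which reproduces the stated 8 weeks. With ±2 days at each end: 195 − 143 = 52 to 199 − 139 = 60.
- Extension: 365 − 309 = 56 days.

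**2. The usual early terminator.**
- Main study: ET at 28 ± 2, so 26 to 30 days. Extension: 28 ± 3, so 25 to 31 days.
- Share of the 56-day window not observed: (56 − 28)/56 = 50%; (56 − 30)/56 = 46% to (56 − 26)/56 = 54% across the main-study visit window.
- An earlier ET visit is allowed, but for subjects who discontinue AK002 Section 10 sets safety contact to day 28 as a minimum.
- Leaving more than 28 days after the last dose: between 28 and 56 days.

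**3. Effect on crude incidence.** Let d be the share of subjects whose collection stops at day 28. Let q be the chance that such a subject's first event of a given type falls in days 29–56 after the last dose. Then

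loss = d × q, and expected subjects missed = 48 × d × q.

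The documents give neither d nor q. The values below are assumptions.

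| d | q | Loss (points) | Subjects of 48 |
|---|---|---|---|
| 5% | 2% | 0.1 | 0.05 |
| 5% | 5% | 0.25 | 0.12 |
| 10% | 10% | 1.0 | 0.48 |
| 20% | 10% | 2.0 | 0.96 |
| 30% | 20% | 6.0 | 2.88 |

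In the middle row about 5 of 48 subjects stop at day 28, and the chance of missing at least one such event is 1 − 0.9^5 = 0.41.

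**4. Direction.** A shorter window cannot raise crude incidence, so any error there is downward. A person-time rate behaves differently. Suppose early terminators stop after Dose 3 (Day 57). They contribute 56 + 28 = 84 days, or 112 with the full window; completers contribute 196. Take one hazard up to 28 days after the last dose and another from day 29. With d = 10% and 20%, the ratio of the observed rate to the full-window rate is:
- equal hazards: 1.00 and 1.00;
- late hazard half the early one: 1.0070 and 1.0148;
- late hazard double: 0.9888 and 0.9765.

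The direction on that scale is therefore not fixed.

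**The case against.** The case on the other side is substantial.

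- **The gap is narrower than it looks.** Section 9.4 follows a subject withdrawn from treatment for an AE until it is resolved or stable. Section 11.6.1 follows clinically significant AEs ongoing at ET, Section 11.6.2 follows unresolved SAEs, and Section 11.6.3 captures pregnancies to 120 days after the last dose. This stands: only new onsets after ET are uncovered.
- **A reader might infer that everyone who stops early has 28 days or less.** The documents do not support that. Section 9.1 provides for later ET visits, the visit window reaches day 30, and Section 10 sets a 28-day minimum for safety contact. Section 9.3 also does not say that collection ends at day 28 for someone who stops drug but stays in the study.
- **A reader might infer that the drug is known to be active beyond day 28.** Section 6.3.1 gives a duration of eosinophil suppression at 0.3 mg/kg only. Longer activity at higher doses is a reasonable inference, not a stated fact.
- **A reader might treat all infections, or delayed hypersensitivity, as AESIs.** Section 11.4 lists opportunistic and parasitic infections and infusion and hypersensitivity reactions; it does not name delayed reactions.
- **Appendix 2 need not contradict Table 9.** The first can be read as the planned follow-up and the second as the exception for ET. The text does not say so, which makes this a matter of wording.
- **Some later data cannot be had.** Consent withdrawal and loss to follow-up are listed routes out of the study. This stands and limits what any fix can recover.
- **This is a descriptive, single-arm pilot without hypothesis tests.** This also stands: no treatment comparison can be distorted.

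None of this supplies a planned collection of new events between ET and 8 weeks after the last dose, or a SAP display of how long each subject was observed after dosing.

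**Conclusion.** The point holds in a limited form. Post-dose collection of new AEs, SAEs and AESIs is unequal: 56 days for completers against usually about 28 for early terminators, in the main study and the extension. The sections on ET timing disagree, and the SAP does not deal with the difference.

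New onsets after ET may be missed, and crude subject incidence may then be understated. It would go too far to say that events are missed or that rates are understated by a known amount, because the documents give no dropout or late-event rate. The range of 0.1 to 6.0 points rests entirely on the assumed d of 5–30% and q of 2–20%. Nor do 1/48 = 2.1 points and 1/12 = 8.3 points measure the gap; they are the weight of any one subject in the whole study or in one cohort. The downward direction applies to the n (%) that the SAP reports, not necessarily to a person-time rate.

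**What to change.** 1. **Collection.** Record new AEs, SAEs and AESIs through 8 weeks after the last dose for every dosed subject, in the main study and the extension. Where the ET visit falls earlier, use one telephone contact at 8 weeks, unless consent is withdrawn or the subject is lost to follow-up. Section 10 already provides for telephone contact with subjects who cannot return.
2. **Protocol wording.** Reconcile the synopsis, Sections 9.1, 9.3, 10, 11, 11.4, 11.5 and 11.6.1, the Appendix 2 summary and Table 9 on when the ET visit takes place and when AE collection ends, separating subjects who stop drug from those who leave the study. Reconcile the 12-week treatment period in Section 10 with dosing to Week 20.
3. **SAP.** Show the length of follow-up after the last dose beside the TEAE table in 7.10.1, for completers and early terminators. Reconcile SAP 5.6, which lists AE reporting at Visits 2–7, with the schedule, which runs to Visit 10.

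The cost is one call per early terminator, amendment wording and one added table line. Reported event rates may rise slightly.

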### **11.1 AE Recording**

At each evaluation, the Investigator or designee will determine whether any AEs have occurred. The assessment of an AE will be done pursuant to definitions set forth by ICH/Good Clinical Practice (GCP) guidelines and other applicable regulatory requirements. The patient will be questioned in a general manner and no specific symptoms will be suggested (e.g., ask the patient if he/she has had any “changes in health” since the last visit or assessment).

Any initial information discovered by the Investigator or designee (i.e., complaint[s] and known start/end dates and times) will be documented. The Investigator or designee will assess the initial AE finding(s) to determine if the medical occurrence is in fact an AE by officially documenting the condition/diagnosis on the AE form.

Action taken will be categorized as none, study drug permanently discontinued, dose modified, required concomitant medication, and/or other.

Event outcome at resolution or time of last follow-up will be recorded as recovered, recovering, not recovered, recovered with sequelae, fatal, or unknown.

